### **9.2 Withdrawal Criteria**

All patients have the right to withdraw any point during the trial without prejudice. The investigator can discontinue any subject at any time if medically necessary. If the ability to monitor the cerebral oximetry is data is lost during the conduct of the study for a significant period of time that precludes useful data analysis then the subject will be withdrawn by the principal investigator.

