- 4) Assess the interventional cohort's preoperative demographics and collected covariates for association with the ease or difficulty of mitigating observed cerebral desaturation events.

Exploratory analyses will include performing all possible comparisons of the two groups based upon all collected perioperative variables to examine the potentially significant relationships between the collected clinical variables representing surrogates of organ perfusion/function and cerebral oximetry desaturations (AUCrSO2). The following exploratory endpoints will be assessed:

- Logistic regression analysis to determine the most relevant AUCrSO2 desaturation value(s) associated with any detrimental clinical outcome(s) monitored in this study
- Logistic regression analysis to determine the most relevant AUC blood pressure values associated with any detrimental clinical outcome(s) monitored in this study
- Comparison of baseline rSO2 values (room air and oxygen supplemented) to all collected clinical variables to assess for possibly significant associations
- Explore the potential impact of rSO2 monitoring on changing the surgical conduct of the procedure

**Methodology:** Single center, prospective, randomized, controlled clinical pilot study

**Number of Subjects:** 100 subjects with balanced randomization (1:1) to control (blinded NIRS data) or intervention (open NIRS data) cohorts

**Main Criteria for Inclusion:** Elderly patients (> 65 years of age) scheduled for a thoracic surgical procedure at UHCMC that will involve SLV.

**Duration of Treatment:** Cerebral oximetry monitoring will begin with an assessment of both room air and oxygen supplemented bi-frontal baseline NIRS values and continue through the surgery to either PACU discharge or the initial 12 hours of post surgical ICU treatment. Mini Mental Status exam testing and Delirium testing with the Confusion Assessment Method will occur preoperatively and postoperatively through post-operative day (POD) #3 (or discharge if that occurs sooner than POD #3).

Enrolled subjects will be followed during the index hospitalization and will undergo a 30 day follow up telephone interview to assess their progress following hospital discharge.

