### **6.2 Primary Objective**

The primary objective of this pilot study is to identify the most relevant clinical outcome variables which significantly diverge as a result of being randomized to the intervention cohort vs. the control cohort so that a larger, multicenter, prospective, randomized controlled clinical trial can be designed to further test the primary hypothesis as stated in the preceding section. The subsequent larger, multicenter trial will be conducted to definitively demonstrate the ability of INVOS® 5100 guided NIRS-based bi-frontal monitoring to improve clinical outcomes in this surgical patient group and potentially establish a new U.S. Food and Drug Administration cleared indication for this monitoring modality.

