## 8.5 Device Image

## 8.6 Device Modification

The subjects randomized to the control group will be monitored with a modified device following the acquisition of the baseline NIRS data. The modification involves electronic blinding of the data via an adjustment made to the device by the manufacturer that prevents the active display of the current data and graphic trends on the display console. However, the modified device will still electronically store the acquired NIRS data for later analysis. The use of this modified version of the device will help to reduce investigator bias that might be introduced if a blinder were affixed to the display console.

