### **10.2 Control Group**

The control group will have both room air and oxygen supplemented baselines obtained in an antecedent fashion to establish that they can produce reliable bilateral cerebral oximetry readings. Because it is known that the device may not be able to produce a valid reading in some individuals with pigmented skin or aberrantly located frontal sinuses this step is necessary to insure that all subjects in the control group will produce useful NIRS data. Once the baseline values have been recorded the cerebral oximetry will be monitored in an electronically blinded manner. Specifically, the device will capture data but neither the current values nor the trend will be displayed on the device's display console. The use of this modified version of the device will help to reduce investigator bias that might be introduced if a blinder were affixed to the display console. The baseline values will be obtained prior to the induction of general anesthesia.

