### **10.3 Intervention Group**

The intervention group will have baseline NIRS values obtained in a manner analogous to the control group. Following recording of the baseline values the subjects will be induced into general anesthesia and the clinicians as well as an IRB registered research assistant will be able to openly monitor the NIRS data. Upon observed cerebral desaturations greater than 20% of the oxygen supplemented baseline on either frontal hemisphere the research assistant will inform the anesthesia clinician that a significant cerebral desaturation is occurring and requires treatment. At this point a standardized interventional protocol will be followed that is detailed in Appendix C. The clinicians caring for the subject will have the ability to override the study intervention algorithm based upon the patient's physical condition at the time.

The intervention protocol for observed desaturations >20% will involve insuring that the subject's head vessels are not kinked or obstructed, increasing the mean arterial pressure via an intravenous fluid bolus or administration of a vasoconstrictor (i.e. phenylephrine or ephedrine) as deemed appropriate by the anesthesia clinician caring for the subject, normalizing PaCO2 to a value between 40 to 50 mmHg, or alternatively normalizing end tidal CO2 to a value of 35 to 45 mmHg. Subsequent interventions may include increasing the FiO2, especially if the SpO2 is below 98% or administering an intravenous inotropic agent if a low flow state is suspected. Administration of an inotrope will occur as judged by the clinician caring for the subject. Finally, in cases where the subject's hematocrit is known or suspected to critically low transfusion of allogeneic blood will be considered. The decision to transfuse allogeneic blood will be made by the anesthesia and surgery clinicians caring for the subject.

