## **15 STATISTICAL PLAN**

All collected data in the case report form will be transferred into a customized electronic database upon completion of the study for the purpose of facilitating statistical analysis.

Preoperative demographics and clinical variables will be compared in the two groups to assess for significant differences using the independent t-test. Differences in the observed clinical data between groups will be determined with the Wilcoxon rank-sum test. Stepwise, forward, multivariable logistic regression analysis will be performed to assess for relationships between cerebral desaturations and any of the measured clinical variables with a p value < 0.05 being considered significant.

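### Section 9.2 withdraws randomised subjects for lost oximetry signal on an unquantified criterion, and section 15 does not say they stay in the between-arm comparison of clinical outcomes

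*Combined protocol and SAP*

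**What the plan says.** Section 9.2 contains two investigator-led removal rules. One is general: "The investigator can discontinue any subject at any time if medically necessary". The other concerns the monitor: when the ability to monitor cerebral oximetry is lost "for a significant period of time that precludes useful data analysis then the subject will be withdrawn by the principal investigator". The second is mandatory. Neither section 9.2 nor any other section gives minutes lost, a share of monitored time, or a one-side or both-sides criterion.

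Randomisation precedes baseline acquisition (sections 7.2.2, 11.2.1 and 11.2.2), so a withdrawal for signal lost during monitoring always falls after randomisation.

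The primary objective (section 6.2) reads, in part: "identify the most relevant clinical outcome variables which significantly diverge as a result of being randomized to the intervention cohort vs. the control cohort". For this comparison section 15 says: "Differences in the observed clinical data between groups will be determined with the Wilcoxon rank-sum test". It names no analysis set, no rule for withdrawn subjects and no missing-data rule.

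On follow-up, the synopsis (Duration of Treatment) says: "Enrolled subjects will be followed during the index hospitalization and will undergo a 30 day follow up telephone interview". Section 9.1 counts its 100 subjects as evaluable, while section 7.1 randomises 100 eligible subjects. Neither evaluability nor replacement is defined.

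On visibility of the signal after baseline, section 10.3 says that in the intervention arm "the clinicians as well as an IRB registered research assistant will be able to openly monitor the NIRS data". Section 10.2 says that in the control arm "the device will capture data but neither the current values nor the trend will be displayed". Section 8.6 adds that "the modified device will still electronically store the acquired NIRS data for later analysis".

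**The concern.** Loss of the rSO2 trace limits what a subject can contribute to the AUC-rSO2 analyses in section 7.4.1. It does not affect whether hospital stay, readmission, delirium, renal change or the composite can be recorded. Section 9.2 nevertheless ties loss of the trace to withdrawal of the whole subject, on the judgement of one person who may know the arm.

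If such subjects then left the clinical comparison, the groups compared might no longer be the groups randomised. The plan allows two routes to trouble, both inferences. First, a failing signal might be noticed and corrected in the arm where it is watched and missed in the arm where it is hidden. Second, monitoring runs to PACU discharge or through 12 hours of ICU care (section 7.2.3), so subjects with longer stays have more time in which to lose signal, and a long PACU stay is itself a component of the composite (section 7.4.1.2).

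The stake is the choice of endpoints for the later multicentre trial. An outcome that appears to diverge because of who was removed could be carried forward.

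**Working it through.** **Reading the sections together.** Three things are certain from the text: withdrawal is mandatory, its threshold is unquantified, and no analysis set is named. What happens to a withdrawn subject's clinical data is not stated anywhere.

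**No plan figure to reproduce.** The documents give 100 subjects without a power calculation, event rate or dropout allowance. They give no withdrawal rate either, so every input below except the 50 per arm is assumed.

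**Inputs.** 50 per arm (100 randomised 1:1, section 7.1); no true effect; adverse outcome rate 50% in both arms (assumed); *w* subjects withdrawn in an arm (assumed); outcome rate *e* among those withdrawn (assumed); withdrawn subjects left out of the analysis (one reading of the plan's silence).

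**Formulas.**
- Observed rate in an arm = (50 × 0.5 − *w* × *e*) / (50 − *w*).
- Difference *d* = intervention − control. SE = square root of the sum over arms of rate × (1 − rate) / number left.
- False-positive rate of a nominal two-sided 5% test = Φ(−1.96 + *d*/SE) + Φ(−1.96 − *d*/SE).

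**Worked case, control 10 v intervention 2, *e* = 80%.** Control: (25 − 8)/40 = 17/40 = 42.5%. Intervention: (25 − 1.6)/48 = 23.4/48 = 48.75%. *d* = 6.25 points, SE = 10.64 points, ratio 0.588. False-positive rate = Φ(−1.372) + Φ(−2.548) = 0.090.

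| Withdrawn, control v intervention | *e* | Observed rates | *d* (points) | False positives |
|---|---|---|---|---|
| 5 v 5 | 80% | 46.7% v 46.7% | 0 | 5.0% |
| 10 v 2 | 50% | 50% v 50% | 0 | 5.0% |
| 3 v 1 | 80% | 48.1% v 49.4% | +1.3 | 5.2% |
| 5 v 1 | 80% | 46.7% v 49.4% | +2.7 | 5.8% |
| 10 v 2 | 65% | 46.25% v 49.4% | +3.1 | 6.0% |
| 10 v 2 | 80% | 42.5% v 48.75% | +6.25 | 9.0% |
| 10 v 0 | 80% | 42.5% v 50% | +7.5 | 11.0% |
| 10 v 2 | 20% | 57.5% v 51.25% | −6.25 | 9.0% |
| 2 v 10 | 80% | 48.75% v 42.5% | −6.25 | 9.0% |

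As a check on the normal approximation, 400,000 simulated trials per case with a tie-corrected Wilcoxon rank-sum test gave 0.090 for 10 v 2 at 80% and 0.050 for 10 v 2 at 50%.

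**Precision, if loss is alike in both arms.** The detectable standardised difference at 80% power is (1.96 + 0.84) × √(2/n). At n = 50 per arm it is 0.56 SD, and at n = 45 it is 0.59 SD. The cost is small.

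**The case against.** The strongest reply is that the plan never says withdrawn subjects are excluded. The synopsis follows enrolled subjects through hospitalisation and a telephone interview. Section 15 opens by moving all collected case-report-form data into the analysis database. Both lean towards keeping what was collected. This stands: exclusion is an inference, and the count in section 9.1 permits it without requiring it.

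Unequal loss by arm is also conjecture. Sections 8.6 and 10.2 hide values and trends but do not say whether signal-status indicators are hidden too. The plan takes steps against loss: bi-frontal baselines are an inclusion criterion (9.1.1), readability is established in both arms before blinding (7.2.2), and section 11.2.4 prescribes skin preparation and adhesive for the pads. Nothing in the documents links signal loss to poor outcome, and 10 v 2 withdrawals have no support there. This stands as well, and it is why the table is only illustrative.

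Finally, this is a pilot with many comparisons, and section 7.4.1 describes its primary endpoints as relationships between oximetry and clinical variables, for which a usable trace is needed. That justifies a completeness rule for the rSO2 analyses. It does not justify withdrawing the subject from a comparison by randomised arm, which section 6.2 makes the primary objective.

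**Conclusion.** The point holds as a defect in the rule and a gap in the analysis plan, and should be fixed. Section 9.2 prescribes a discretionary removal after randomisation, on an unquantified criterion, for a reason unrelated to the clinical outcomes. Section 15 does not secure those subjects' place in the comparison. Confidence in that is high, because it rests on the text.

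The size of any bias is unknown. It is zero if loss is uninformative or alike in both arms. Under the stated assumptions it runs from 1.3 points (3 v 1) to 6.25 points (10 v 2) at an 80% outcome rate among those withdrawn. It can go either way, and 10 v 0 gives 7.5, so none of these figures is a bound.

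A reader might infer more than the documents support:
- **That the plan excludes withdrawn subjects from analysis.** It is silent, and some text leans the other way.
- **That the control arm will lose more signal.** Hidden values make this possible but do not show it.
- **That testing inclusion criteria 2 to 4 after the envelope is opened biases the arms.** Both arms have the same open baseline, so this would need the criteria to be applied differently by arm, and nothing says they are. No change to the order of randomisation is asked for here.

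**What to change.** 1. Amend section 9.2 so that loss of oximetry signal is handled as missing rSO2 data and limits only that subject's part in the rSO2 analyses. Fix a numeric completeness threshold in advance. Apply it blind to arm from the stored INVOS files, which exist in both arms (section 11.3.2 has PICIS recording rSO2 in the intervention group only). Report the amount of lost data and the exclusions from rSO2 analyses by arm.
2. State in section 15 that clinical outcomes are compared in all randomised subjects by assigned arm, using every outcome collected, including for subjects discontinued under section 9.2. Follow-up continues unless consent is withdrawn. Report the number analysed per arm for each outcome.

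As a minor wording point, align the randomised count in section 7.1 with the evaluable count in section 9.1.

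These are text changes with no added visits, since follow-up and device storage are already planned. The cost is that some subjects with incomplete rSO2 traces stay in the clinical comparison. A subject without a baseline MMSE still cannot contribute a change score. The investigator's clinical discretion is unchanged, because the amendment governs data and analysis only.

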## **10 TREATMENT OF SUBJECTS**

### **10.1 Study Device**

The study device, INVOS® 5100C, is described in Section 8. Enrolled subjects will be randomized in a balanced fashion (1:1) to either the control group (blinded cerebral oximetry monitoring intraoperatively and in the immediate postoperative period) or to the intervention group (open cerebral oximetry monitoring with the use of a standardized intervention protocol for observed desaturations greater than 20%).

### **10.2 Control Group**

The control group will have both room air and oxygen supplemented baselines obtained in an antecedent fashion to establish that they can produce reliable bilateral cerebral oximetry readings. Because it is known that the device may not be able to produce a valid reading in some individuals with pigmented skin or aberrantly located frontal sinuses this step is necessary to insure that all subjects in the control group will produce useful NIRS data. Once the baseline values have been recorded the cerebral oximetry will be monitored in an electronically blinded manner. Specifically, the device will capture data but neither the current values nor the trend will be displayed on the device's display console. The use of this modified version of the device will help to reduce investigator bias that might be introduced if a blinder were affixed to the display console. The baseline values will be obtained prior to the induction of general anesthesia.

### **10.3 Intervention Group**

The intervention group will have baseline NIRS values obtained in a manner analogous to the control group. Following recording of the baseline values the subjects will be induced into general anesthesia and the clinicians as well as an IRB registered research assistant will be able to openly monitor the NIRS data. Upon observed cerebral desaturations greater than 20% of the oxygen supplemented baseline on either frontal hemisphere the research assistant will inform the anesthesia clinician that a significant cerebral desaturation is occurring and requires treatment. At this point a standardized interventional protocol will be followed that is detailed in Appendix C. The clinicians caring for the subject will have the ability to override the study intervention algorithm based upon the patient's physical condition at the time.

The intervention protocol for observed desaturations >20% will involve insuring that the subject's head vessels are not kinked or obstructed, increasing the mean arterial pressure via an intravenous fluid bolus or administration of a vasoconstrictor (i.e. phenylephrine or ephedrine) as deemed appropriate by the anesthesia clinician caring for the subject, normalizing PaCO2 to a value between 40 to 50 mmHg, or alternatively normalizing end tidal CO2 to a value of 35 to 45 mmHg. Subsequent interventions may include increasing the FiO2, especially if the SpO2 is below 98% or administering an intravenous inotropic agent if a low flow state is suspected. Administration of an inotrope will occur as judged by the clinician caring for the subject. Finally, in cases where the subject's hematocrit is known or suspected to critically low transfusion of allogeneic blood will be considered. The decision to transfuse allogeneic blood will be made by the anesthesia and surgery clinicians caring for the subject.

## **11 PROTOCOL ASSESSMENTS AND PROCEDURES**

The Schedule of Assessments which details the sequence of assessments and procedures is presented in Table 1. Note that as described in Section 7.2 there are four separate periods that this study is divided into that include the following: screening, baseline, intraoperative and immediate postoperative and postoperative follow up.

Table 1: Schedule of Assessments

	Screening	Baseline Acquisition	Intraoperative and Immediate Postoperative	Postoperative Follow Up
Study Assessment				
Review of inclusion/exclusion criteria	X			
Informed consent	X			
Demographics	X			
Medical history	X			
Randomization		X		
MMSE & CAM testing		X		X
Serum creatinine	X			X
Obtain baseline room air and O 2 supplemented rSO 2		X		
Continuous rSO 2 , SpO 2 , blood pressure data collection			X	
Employ rSO 2 desaturation algorithm (intervention group only)			X	
Continuous intra/immediate post-operative clinical variable collection			X	
PACU and ICU clinical variable collection			X	
Postoperative clinical variable collection			X	X
Adverse and Serious Adverse Event Monitoring		X	X	X
Telephone interview				X

## **11.1 Protocol Assessments and Procedures – Screening Period**

### **11.1.1 General Screening Period Description**

Screening of potential subjects will occur prior to the planned surgical procedure to allow individuals time to consider their participation. Subjects will be screened from the daily Mather Operating Room printed schedule. Subjects scheduled to undergo surgical procedures that appear to meet the primary inclusion criteria will be approached for additional screening in the Mather Preoperative Area. An IRB registered investigator or nurse coordinator will approach the patient if they are willing to consider listening to a brief description of the study. Patients who verbally agree to learn more about the study will then have a discussion with the IRB registered study investigator or nurse coordinator which includes the details of the study explained in clear and concise language. During this conversation the voluntary nature of any individual's participation will be clearly communicated. Additionally, the discussion will include a description of what the patient's participation will entail, including the voluntary nature of their participation, their ability to withdraw at any time, the confidential nature of their participation, the procedures that will occur among study participants, the information that will be collected from participants and all of the risks and benefits associated with their participation in the trial. Additionally, the study staff will explain to the patient how their hospital care may be different if they choose to participate in the study, including the fact that they will be randomized to either the control group or the intervention group with a 50% chance of being assigned to either group. The implications of being assigned to either group will be discussed.

### **11.1.2 Informed Consent**

Patients will also be given the opportunity to ask questions of the study investigator or nurse coordinator and express their personal concerns about what their participation may entail. If the patient wishes to participate then the study investigator will then review the study consent form in a page-by-page manner to insure that they understand all aspects of what their participation will include. At this point additional time to personally review the consent form document will be given to each potential subject. Following this, potential participants will then be given another opportunity to ask questions and once all of them have been satisfactorily addressed the subject and the study investigator will sign, time and date the consent form. A copy of the consent will be placed in the patient's chart and given to the patient's family/escort or will be secured and given to the patient after their surgical procedure.

